CLINICAL STUDY PROTOCOL

TITLE: A Single-center, Retrospective Study to Evaluate the Clinical Performance of Artificial Intelligence Medical Assisted Diagnostic Software (VeriSee AMD) for Screening of Age-Related Macular Degeneration

Protocol Number: AHCI21001

Phase of Study: Pivotal study

Version No: 1.2

Version Date: 16-Jul-2021

Sponsor: Acer Medical Inc.

Sponsor Address: [name]

Confidentiality Statement

The information in this document contains trade secrets and commercial information that are privileged or confidential and may not be disclosed unless such disclosure is required by applicable laws and regulations. In any event, persons for whom this information is disclosed must be informed that the information is privileged or confidential and may not be further disclosed by them. These restrictions on disclosure will apply equally to all future information supplied to you that is indicated as privileged or confidential.

Clinical Study Protocol

Title:

A Single-center, Retrospective Study to Evaluate the Clinical Performance of Artificial Intelligence Medical Assisted Diagnostic Software (VeriSee AMD) for Screening of Age-Related Macular Degeneration.

Objectives:

This study is to evaluate the clinical performance of VeriSee AMD for AMD screening from color fundus photography images. The sensitivity and specificity of VeriSee AMD's automated image analysis for screening the age-related macular degeneration will be determined.

Investigational product:

1. Name: VeriSee AMD
2. Model: AMD-01
3. Manufacturer: Acer Medical Inc.
4. Method of analysis: VeriSee AMD is a software as medical device that incorporates an artificial intelligence (AI)-based algorithm to evaluate the age-related macular degeneration (AMD) from color fundus photography images screening. The screening result of AMD will be determined as non-more than level 3 AMD (non-mtl3AMD) or more than level 3 AMD (mtl3AMD).
5. Intended use: VeriSee AMD is intended to screen AMD from the images taken by color fundus photography, which can assist the physicians to assess whether further examination for retinopathy by the ophthalmologist is needed. The screening result of AMD will be determined as non-mtl3AMD or mtl3AMD. VeriSee AMD only provides the screening results of AMD for the physicians' reference and VeriSee AMD is not intended to diagnose of AMD, detect concomitant diseases, or treat AMD.

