6. Device type: Software as a medical device (SaMD)

Clinical Study Protocol

Endpoints:**1. Primary endpoint:**

- To evaluate the clinical performance of VeriSee AMD by determining the sensitivity and specificity.

2. Secondary endpoints:

- To evaluate the clinical performance of VeriSee AMD by determining the positive and negative predictive values (PPV and NPV)
- To determine the percentage of subjects' images with insufficient quality as judged by VeriSee AMD

Selection criteria:

The screening by inclusion and exclusion criteria for eligibility of subjects will be performed by the information technology office at the clinical site. A dedicated ophthalmologist will be responsible to confirm the eligibility of enrolled subjects' color fundus photography images for inclusion criterion # 3 and exclusion criterion # 2.

1. Main inclusion criteria:

(1) Subject with age \geq 50 years old

(2) Subject with image taken by Canon CR-2 that meet the following requirement:

- The resolution of image is 271 \times 271 pixels or higher.
- The angle view of image is 45 or 50 degrees.

(3) Subject's image includes macula as judged by the ophthalmologist.

2. Main exclusion criteria:

(1) The color fundus photography image previously used by VeriSee AMD during the development process and pre-clinical test

(2) The macula or other part in the image of color fundus photography is unclear to determine the disease condition as judged by the ophthalmologist.

Clinical Study Protocol**Study procedures:**

This is a single-center, retrospective study to evaluate the performance of VeriSee AMD for screening of potential age-related macular degeneration (AMD). The sensitivity and specificity of VeriSee AMD will be determined in this study by comparing the results of gold standard, which is the judgment of AMD by the ophthalmologists (evaluators).

Age-Related Macular Degeneration Severity Scale (AMD Severity Scale)	
AMD Level	Criteria
1	Drusen maximum size < circle C-0 (63 µm diameter) and total area < circle C-1 (125 µm diameter)

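### Exclusion (1) bars the development image but does not settle whether it also bars the person, so other images of the same people may enter the test set

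*Protocol*

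**What the plan says.** Under Selection criteria, the lead-in states: "The screening by inclusion and exclusion criteria for eligibility of subjects will be performed by the information technology office at the clinical site". Separately, an ophthalmologist is to "confirm the eligibility of enrolled subjects' color fundus photography images for inclusion criterion # 3 and exclusion criterion # 2", and nothing else.

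The first item under "2. Main exclusion criteria" is: "The color fundus photography image previously used by VeriSee AMD during the development process and pre-clinical test". It does not mention the subject, the fellow eye or other visits. By contrast, the second inclusion criterion is worded on the person: "Subject with image taken by Canon CR-2 that meet the following requirement".

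The title block carries "Phase of Study: Pivotal study", and Study procedures begins "This is a single-center, retrospective study to evaluate the performance of VeriSee AMD". The Endpoints section makes sensitivity and specificity the primary endpoint. The text at hand does not say where the development or pre-clinical images came from, nor how many images or eyes per subject are tested.

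**The concern.** The evident purpose of exclusion (1) is to keep the test set separate from the data on which the algorithm was built and tried out. Two eyes of one person, or two visits of the same eye, are not independent. A rule that removes only the image already used can therefore leave closely related images of the same person in the test set.

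If that happens, part of the test material is not new to the algorithm, and sensitivity and specificity may be overestimated. The information technology office must match on either an image identifier or a subject identifier. The two give different test sets whenever a development subject has another eligible image, and the protocol does not say which to use.

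**Working it through.** **Step 1: does any listed criterion settle the unit or close the gap?** The protocol gives no figure on this point, so the first check is of the text.

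| Listed main criterion | What it concerns | Keeps out another image of a development subject? |
|---|---|---|
| Inclusion (1) | Age | No |
| Inclusion (2) | Camera, resolution, angle of view | No |
| Inclusion (3) | Macula in the image | No |
| Exclusion (1) | Image used in development or pre-clinical test | Only on a subject-level reading |
| Exclusion (2) | Image clarity | No |

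The ophthalmologist's check covers inclusion (3) and exclusion (2) only, so it does not reach exclusion (1). No sentence chooses between the image reading and the subject reading.

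**Step 2: how large could the effect be on the literal reading?** All three inputs are assumptions; none stands in the document.

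- p: share of archive images used in development or pre-clinical testing, picked image by image and independently.
- k: images per subject.
- d: accuracy on people already seen minus accuracy on unseen people, in percentage points.

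The share of test material from already-seen people depends on the unit tested, which the text does not fix.

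- Counting eligible (unused) images: at least one of the subject's other k-1 images was used, so f = 1 - (1-p)^(k-1).
- Counting eligible subjects, with one image tested for each: a subject is eligible if not all images were used (probability 1 - p^k), and is an overlap case if some but not all were used. So g = [1 - p^k - (1-p)^k] / (1 - p^k).

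Example, p = 10%, k = 2: f = 1 - 0.9 = 10.0%; g = (1 - 0.01 - 0.81)/(1 - 0.01) = 0.18/0.99 = 18.2%.

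Example, p = 10%, k = 4: f = 1 - 0.729 = 27.1%; g = (1 - 0.0001 - 0.6561)/0.9999 = 34.4%.

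| p | f, k=2 | g, k=2 | f, k=4 | g, k=4 |
|---|---|---|---|---|
| 0 | 0 | 0 | 0 | 0 |
| 5% | 5.0% | 9.5% | 14.3% | 18.5% |
| 10% | 10.0% | 18.2% | 27.1% | 34.4% |
| 20% | 20.0% | 33.3% | 48.8% | 59.0% |

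**Step 3: shift in sensitivity or specificity.** If A is the accuracy on unseen people and s the share already seen, the expected estimate is (1-s)A + s(A+d) = A + s × d. The shift is therefore s × d, with s taken among the diseased for sensitivity and among the non-diseased for specificity.

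| Setting | d = 0 | d = 2 | d = 5 | d = 10 |
|---|---|---|---|---|
| p=10%, k=2, images | 0 | 0.2 | 0.5 | 1.0 |
| p=10%, k=2, subjects | 0 | 0.4 | 0.9 | 1.8 |
| p=20%, k=4, images | 0 | 1.0 | 2.4 | 4.9 |
| p=20%, k=4, subjects | 0 | 1.2 | 2.9 | 5.9 |

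Over the whole grid the shift runs from 0 to 4.9 points (images) or 0 to 5.9 points (subjects). It is zero if the development data came from other patients, if all images of each development subject were used together, or if d = 0.

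**The case against.** The strongest reply is that context favors the subject reading. The information technology office screens subjects, the ophthalmologist confirms images, and exclusion (1) falls on the office's side. Exclusion (2) is also worded on the image under the same lead-in, so the image wording may be drafting shorthand. This is a fair reading, but it does not settle the matter: an office screening an archive can filter by image file just as easily as by person.

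Second, the list is headed as the main criteria, so a fuller list may exist outside the text at hand. That limit stands.

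Third, harm needs a chain that is not shown: development images from this site's patients, another eligible image of such a patient, its selection, and better accuracy on seen people. An exclusion written as a precaution does not prove a shared source. This also stands, and it is why overlap is called possible and no bias is claimed. The upper ends of the grid need p = 20%, k = 4 and d = 10 together, and the document supports none of these; the grid shows a range and is not evidence.

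Fourth, overlap could be checked later and performance re-estimated without those subjects. That works only if identifiers can be linked, and a clear rule at selection is simpler.

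**Conclusion.** The concern holds. Exclusion (1) is worded on the image, the subject-level lead-in makes a subject reading possible but does not fix it, and no other listed main criterion keeps out a fellow-eye or other-visit image of a development subject. The ambiguity in the text is certain.

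Its effect on sensitivity and specificity is unknown and possibly zero. The illustrative range depends wholly on assumed p, k and d and on independent picking of images, and the judgment that this should be fixed does not rest on it. It rests on the independence of the test set, which underlies both primary measures and which the wording as it stands does not secure. Confidence is moderate, given the limits on the source of the images and on the completeness of the list.

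**What to change.** Reword exclusion (1) at the level of the person: *any subject with one or more images (either eye, any visit) used in VeriSee AMD development or pre-clinical testing*. State that the site's information technology office applies it by matching on subject identifier.

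If identifiers cannot be linked, confirm and state in the protocol that the development and pre-clinical data came from other patients. That works only where the source was demonstrably separate. If the images came from this site and cannot be linked, neither route secures independence, and the protocol should state this as a limitation.

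The cost is a one-sentence amendment and an identifier match. Overlapping subjects are lost and must be replaced: none if there is no overlap, and 18.2% of otherwise eligible subjects (10.0% of otherwise eligible images) under the assumed p = 10%, k = 2. The match needs development images that can be traced to subject identifiers, which the document does not state.

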2	
Presence of one or more of the following:
 
 (a) Drusen maximum size \geq circle C-0 but < circle C-1 (b) Drusen total area \geq circle C-1 (c) Retinal pigment epithelial pigment abnormalities consistent with AMD, defined as one or more of the following in the central or inner subfields: 
 (1) Depigmentation present (2) Increased pigment \geq circle C-1 (3) Increased pigment present and depigmentation at least questionable
3	
Presence of one or more of the following:
 
 (a) Drusen maximum size \geq circle C-1 (b) Drusen maximum size \geq circle C-0 and total area $>$ circle I-2 and type is soft indistinct (c) Drusen maximum size \geq circle C-0 and total area $>$ circle O-2 and type is soft distinct (d) Geographic atrophy within grid but none at center of macula
4 (Advanced)	
Presence of one or more of the following:
 
 (a) Geographic atrophy in central subfield with at least questionable involvement of center of macula (b) Evidence of neovascular AMD 
 (1) Fibrovascular/serous pigment epithelial detachment (2) Serous (or hemorrhagic) sensory retinal detachment (3) Subretinal/subretinal pigment epithelial hemorrhage (4) Subretinal fibrous tissue (or fibrin) (5) Photocoagulation for AMD

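### Exclusion criterion (2) lets one ophthalmologist pre-clear images with no technical standard, so accuracy is likely overstated and the insufficient-quality rate likely understated for the intended use

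*Protocol*

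**What the plan says.** Under Selection criteria, Main exclusion criteria (2), an image is dropped if "The macula or other part in the image of color fundus photography is unclear to determine the disease condition as judged by the ophthalmologist". The paragraph introducing the criteria says who decides: "A dedicated ophthalmologist will be responsible to confirm the eligibility of enrolled subjects' color fundus photography images", for inclusion criterion 3 and exclusion criterion 2. The site's information technology office screens for eligibility.

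Under Endpoints, the primary aim is "To evaluate the clinical performance of VeriSee AMD by determining the sensitivity and specificity". A secondary endpoint is the percentage of subjects' "images with insufficient quality as judged by VeriSee AMD". Under Study procedures, the reference standard is the evaluating ophthalmologists' own judgement of AMD; no other reference is named.

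Under Investigational product, item 5, "VeriSee AMD is intended to screen AMD from the images taken by color fundus photography", to help physicians decide whether an ophthalmologist should examine the patient further. That statement does not confine use to images an ophthalmologist has already found clear.

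**The concern.** The test in criterion (2) is whether a reader can determine disease. It gives no definition of an unclear image, no list of defects and no statement of which area must be readable. One person applies it, ahead of the reference grading.

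Two things are at stake. First, images that an expert finds hard to read are those on which software and evaluators are most likely to disagree. Removing them first selects an easier set for the primary endpoint of a pivotal study, through a step that does not exist in screening practice. Second, the software has its own insufficient-quality output, and its frequency is an endpoint. If a human has already removed the poor images, that frequency no longer describes what users of the software will meet.

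**Working it through.** **Setting the passages side by side**

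- *Doubtful grades.* What must be unclear is a part of the image, but the yardstick is determination of disease. The severity scale under Study procedures turns on fine limits (drusen size against circle C-1, questionable involvement of the macular centre). A reader who sets aside an image because the level is in doubt could still claim to comply.
- *'Or other part'.* Several scale criteria are confined to the macula, the grid or the central and inner subfields, for instance level 3(d): "Geographic atrophy within grid but none at center of macula". The criterion does not say which other parts count.
- *Order of steps.* Eligibility comes before both the reference grade and the software result, so the filter acts on the primary endpoint and on the insufficient-quality percentage.

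**Size.** The Protocol shown gives no expected accuracy, exclusion rate or software rejection rate, so there is no figure to reproduce. Every input below is an assumption.

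*1. Accuracy, if the software grades every image.* Let e be the share of otherwise eligible images removed (among diseased eyes for sensitivity, non-diseased for specificity), and A_clear and A_unclear the accuracy in kept and removed images.

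Accuracy in all images = (1 − e) × A_clear + e × A_unclear, so overstatement = e × (A_clear − A_unclear).

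Overstatement in percentage points, with A_clear = 0.90:

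| e | A_unclear = 0.50 | A_unclear = 0.70 | A_unclear = 0.90 |
|---|---|---|---|
| 5% | 2.0 | 1.0 | 0 |
| 10% | 4.0 | 2.0 | 0 |
| 20% | 8.0 | 4.0 | 0 |

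With A_clear from 0.85 to 0.95 and A_unclear from 0.50 to 0.70, the extremes are 0.05 × (0.85 − 0.70) = 0.75 points and 0.20 × (0.95 − 0.50) = 9.0 points.

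*2. Accuracy, if the software rejects most unclear images.* Take e = 10%, A_clear = 0.90, A_unclear = 0.70, and 90% of unclear images rejected. For simplicity no clear image is rejected. The study reports 90.0%.

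- Rejects leave the table: (0.90 × 0.90 + 0.10 × 0.10 × 0.70) / (0.90 + 0.10 × 0.10) = 0.817 / 0.91 = 89.8%. Almost no overstatement.
- Rejects count as referrals: sensitivity in all images = 0.81 + 0.10 × (0.90 + 0.10 × 0.70) = 90.7%; specificity = 0.81 + 0.10 × 0.10 × 0.70 = 81.7%. Reported sensitivity is then slightly too low and reported specificity too high.

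*3. Insufficient-quality percentage.* Suppose the software rejects 2% of clear images and 50% to 90% of unclear ones. The study sees only clear images and reports 2.0%. Over all images the rate is (1 − e) × 0.02 + e × r, with r = 0.50 to 0.90:

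| e | Reported | All images |
|---|---|---|
| 5% | 2.0% | 4.4% to 6.4% |
| 10% | 2.0% | 6.8% to 10.8% |
| 20% | 2.0% | 11.6% to 19.6% |

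This direction holds whenever the software rejects excluded images more often than kept ones.

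**The case against.** The strongest reply is that criterion (2) is an ordinary gradability rule, and one the design needs. The only reference is the evaluators' reading of the image, so an image nobody can grade has no reference result and cannot enter sensitivity or specificity. That stands. Deleting the criterion would not repair the estimates, and the fix keeps an exclusion for ungradable images.

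Three stronger readings are tempting, and the text does not support them.

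- A reader might infer that sharp images with borderline AMD are excluded. The subject of the criterion is an unclear macula or other part, so on the ordinary reading a sharp image with drusen near a size limit stays in. The wording permits its exclusion but does not require it.
- A reader might infer that any blur outside the macula excludes an image. 'Or other part' is qualified by the need to determine the disease condition, so blur that does not hinder grading need not exclude. The phrase is loose rather than plainly wrong.
- A reader might state as fact that both accuracy measures are inflated, by some 1 to 6 points. Such a figure follows from assuming 92% sensitivity in clear-cut positives, 60% to 70% in borderline ones, and a borderline share b of 5% to 20%: b × (0.92 − s), or 1.1 points at b = 0.05, s = 0.70 and 6.4 points at b = 0.20, s = 0.60. The arithmetic is right, but every input is assumed, and it presumes that all borderline positives are removed.

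Nor does the Protocol suggest that the eligibility reader sees the software's output, so no such fault is alleged.

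**Conclusion.** The point holds as one of selection and loose wording. From the text alone, a single reader filters images before reference grading, on a subjective test with no technical standard, and the intended use has no such step. The accuracy results will therefore apply only to pre-cleared images.

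That sensitivity and specificity are overstated for the intended use is the expected direction but is not proven. It assumes that the software does worse on the excluded images and would not itself reject most of them. The size cannot be obtained from the Protocol.

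The firmer consequence is for the secondary endpoint. The insufficient-quality percentage is likely understated, because poor images are removed before the software can reject them; its size is also unknown. The change is cheap and should be made.

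**What to change.** 1. Limit exclusion (2) to technical image defects (blur, exposure, artefact, obscured macula) that prevent grading of the macular area the severity scale needs. Tie 'or other part' to that area, or delete it.
2. State that doubt about the AMD level is not a reason to exclude, and that such images go to the planned evaluators for a reference grade.
3. Run the software on all images that meet the other criteria, and compute the insufficient-quality percentage on that set, before this exclusion is applied.
4. Report how many images exclusion (2) removes, with the reason for each.

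Cost: one criterion reworded, one denominator defined, and software runs on images that would otherwise be discarded. No new readers are needed, since the same ophthalmologist applies a narrower rule. The evaluators will face some harder images, and the accuracy figures may come out slightly less favourable. Images that still cannot be graded stay outside sensitivity and specificity, but their number will be known.
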